By my signature below, I agree to conduct this Study in accordance with the Clinical Trial Protocol, current Good Clinical Practice (cGCP) and Good Laboratory Practice (cGLP) guidelines, obligations as set forth in Title 21 CFR Parts 812, 54, 5,6 and 11 (as applicable), and any applicable regulatory laws. I will make no changes to protocol-defined procedures without written permission from the Sponsor.

I understand that Investigational Use Products may be used **only** for the purposes explicitly described in this protocol.

I further agree to treat the results of this Study as confidential information and will not submit the results of the Study for publication without prior written authorization from the Sponsor.

[name]

PRINTED NAME

SIGNATURE

7/15/2021

DATE

SYNOPSIS

Title of Study	Phase I study to examine the safety and efficacy of allogeneic MSCs in suppressing inflammation in patients with small abdominal aortic aneurysm (AAA)
Objectives	Assess the safety and efficacy of systemic (IV) administration of escalating doses of allogeneic MSCs in modulating immune cell phenotypes and suppressing aortic inflammation in patients with small AAA.
Planned Number of Subjects and Duration of Involvement	36 patients
Patient Population	Abdominal aortic aneurysms (AAA) patients
Investigational Product Name	Allogeneic mesenchymal stem cells
Methodology Overview	In a double blind, Phase I trial, 36 patients with AAA measuring 30-50mm in maximal transverse diameter (MTD) will be randomized in a 1:1:1 fashion to receive either 1.0×10^6 MSCs/kg (n=12), 3.0×10^6 MSCs/kg. (n=12), or placebo (Plasmalyte A) (n=12) delivered intravenously. The primary safety endpoints will be incidence of treatment related adverse events at 24 months post MSC-administration. Exploratory primary efficacy endpoints will be changes in circulating inflammatory cell phenotypes and aortic inflammation as measured by CT. The treatment period will involve long-term follow-up through 5 years. The incidence of surgical intervention, aneurysm related death, quality of life, and major adverse cardiac events will be recorded.

Table 1 Abbreviations

AAA	Abdominal Aortic Aneurysm
AE	Adverse Event
AMI	Acute Myocardial Infarction
ASC	Adipose derived MSC
bMSC	Bone marrow derived MSC
CTSI	Clinical and Translational Sciences Institute
DSMB	Data Safety Monitoring Board
eGFR	Effective Glomerular Filtration Rate
GVHD	Graft Versus Host Disease
IFN- γ	Interferon- γ ,
IL	Interleukin

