The objective of this study is to conduct a single center, double blind, Phase I trial to test the safety of systemic (intravenous, IV) administration of allogeneic bone marrow derived MSCs and compare two doses (1 million and 3 million MSCs/kg. in modulating inflammatory responses in patients with small AAA. The rationale for this investigation is: (1), there are no effective treatment options that suppress AAA inflammation and expansion; (2), there is an established safety profile of MSCs in previous clinical trials⁷⁻¹¹; and (3), compelling preliminary data supporting this concept.

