9. STATISTICAL METHODS

The safety of systemic administration of allogeneic MSCs will be measured by treatment-related adverse events. Treatment-related adverse events will be categorized by overlapping systems and severities. The three categories of systems are cardiovascular, respiratory, or infectious. Two categories of severity will be serious adverse (SAE) and major adverse cardiac events (MACE). For completeness, instances of adverse events may appear in more than one category. Within each of these categories adverse events will be listed in descending order of frequency for the treatment-group. In addition, for each category, the sum and difference between the two routes of delivery of the proportions will be reported as percent incidence. Confidence Intervals at the 95% confidence level and *P*-values for these four groups will be calculated. Since four previous trials have not reported adverse events with MSC treatment, confidence intervals will be generated by the method of the Wilson Score Interval because they are robust, with good coverage probability even for small number of trials and are not degenerate near zero. These intervals will be used to summarize the data rather than as any formal inferential statement. No adjustment for multiplicity will be made.

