Primary attention in Aim 1 will focus on the detection of cellular immunosuppression activity coincident with MSC administration in both proliferation (six decreasing and one increasing) and function (three decreasing functional outcomes). Ten mixed model repeated measures with a fixed term for MSC dose and their appropriate baseline covariate will be fit. The denominator degrees of freedom will be estimated by the method of Kenward and Rodger.¹² A compound symmetry covariance structure will be fit if the model with the unstructured covariance does not converge. For these data the directionality of superiority or inferiority will be assessed. Specifically, the alternative hypotheses are that (1) three T-cell counts (CD4⁺CD28⁻, CD8⁺CD28⁻ T-cells and Th-17⁺ T-cell) will be decreased; (2) CD28⁻ T-cell function will be inhibited (decreased; as measured by IFN- γ -producing cells, Perforin-producing cells, and CD57 expression); (3) T-regulatory cells (CD4⁺Fox3P⁺ T-regs) will be increased; and (4) monocytes will be decreased (fewer CD45⁺CD14⁺⁺CD16⁻, CD45⁺CD14⁺CD16⁺, CD45⁺CD14dim/CD16⁺⁺). To assess the individual hypotheses, the model-derived, confidence interval for the intercept will be reported. Confidence intervals at the 95% level from the same models will be constructed to estimate the difference, or contrast, between routes of administration

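### The ten Aim 1 hypotheses are judged by the model intercept, which is never an arm comparison; no contrast with placebo is named, and the one contrast named is between routes in an all-IV trial

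*Combined protocol and SAP*

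**What the plan says.** Section 9 (Statistical Methods) describes the Aim 1 models: "Ten mixed model repeated measures with a fixed term for MSC dose and their appropriate baseline covariate will be fit". It lists ten directional alternatives, nine decreases and one increase, and adds: "For these data the directionality of superiority or inferiority will be assessed". The rule for judging them is: "To assess the individual hypotheses, the model-derived, confidence interval for the intercept will be reported". The next sentence takes 95% intervals from the same models, which "will be constructed to estimate the difference, or contrast, between routes of administration". Neither the coding of dose nor the scale of the outcome is stated there.

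The safety paragraph of section 9 has parallel wording: "the sum and difference between the two routes of delivery of the proportions will be reported as percent incidence", with intervals and P-values that "for these four groups will be calculated".

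The design is different. The Synopsis and sections 6.1.2, 6.1.4 and 7.1 describe three arms (placebo, 1 million and 3 million MSCs/kg), all given intravenously. The Introduction says the trial will "compare two doses (1 million and 3 million MSCs/kg. in modulating inflammatory responses in patients with small AAA", and section 3.4 states a dose-dependence hypothesis. The Synopsis gives the status of the outcomes: "Exploratory primary efficacy endpoints will be changes in circulating inflammatory cell phenotypes and aortic inflammation as measured by CT".

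**The concern.** The trial randomises against a concurrent placebo and asks whether dose matters. The quantity that section 9 uses to judge each hypothesis answers neither question. Followed exactly, the rule lets a change that occurs in every arm look like support for MSCs. A real MSC effect may be invisible or obvious depending only on which arm the software takes as reference.

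A shared change is plausible. For example, section 6.1.4 describes hydrocortisone premedication without distinguishing arms. The documents give no indication of how large any shared change would be.

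The contrast that could have repaired this is labelled by route, and route does not vary in this trial. Section 3.4 says the results will direct a Phase II trial, so a misread cell outcome could carry forward.

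**Working it through.** **Inputs from the documents.** Three arms of 12, all IV (Synopsis). Ten outcomes: 3 T-cell counts + 3 CD28- functions + 1 Treg + 3 monocyte subsets = 10. This matches the plan's own split of 6 + 1 + 3 = 10.

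**Assumed scale.** Section 9 does not state the outcome scale. The Synopsis and section 3.4 define efficacy as change, so I take change from baseline with a centred baseline covariate. With a raw outcome and an uncentred baseline, the intercept would be an extrapolation to a baseline of zero, which is no more useful.

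**Step 1: general result.** If all three arm means equal c, the intercept equals c. Its weights on the arm means therefore sum to 1. An arm contrast needs weights that sum to 0.

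**Step 2: weights by coding.** For dose entered as a number (0, 1, 3), the mean dose is 4/3 and the sum of squares is 10 - 16/3 = 14/3. The weight at dose x is 1/3 - (4/3)(x - 4/3)/(14/3) = 1/3 - (2/7)(x - 4/3), which gives 5/7, 3/7 and -1/7.

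**Step 3: what each coding estimates.** Let d be a change common to all arms and e an additional effect equal in both MSC arms, so the arm means are (d, d+e, d+e).

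| Quantity | Weights (placebo, 1M, 3M) | Estimates | d=-0.5, e=0 | d=0, e=-1 |
|---|---|---|---|---|
| Intercept, placebo reference | (1, 0, 0) | d | -0.5 | 0 |
| Intercept, 3M reference | (0, 0, 1) | d + e | -0.5 | -1 |
| Intercept, effect coding | (1/3, 1/3, 1/3) | d + 2e/3 | -0.5 | -0.67 |
| Intercept, numeric dose | (5/7, 3/7, -1/7) | d + 2e/7 | -0.5 | -0.29 |
| 3M minus placebo | (-1, 0, 1) | e | 0 | -1 |

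Every intercept contains d in full. The contrast removes it.

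**Step 4: illustration, all inputs assumed.** Complete data, 12 per arm, unit SD at each visit, and the 7 post-infusion blood draws to Month 24 in Table 2 (Table 3 adds 6 more, 13 in all; section 9 does not say which are used). Compound symmetry with correlation 0.5/0.7/0.85. The mean change over visits is regressed on arm and centred baseline, with 32 residual df (33 for numeric dose).

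The variance of the visit mean given baseline is (1-r)/7 + r - r², which is 0.321/0.253/0.149. The standard error of 3M minus placebo is the square root of (variance × 2/12), which is 0.231/0.205/0.158. For an effect of -1 SD, the noncentral t gives power 98.7/99.7/100%.

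Simulated share of trials with the 95% interval wholly below zero (nominal 2.5% when the true value is zero), at correlation 0.5/0.7/0.85:

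| Quantity | No effect, no drift | No effect, drift -0.5 SD | Effect -1 SD, no drift |
|---|---|---|---|
| Intercept, placebo reference | about 3-4% | 81/90/99% | about 3-4% |
| Intercept, effect coding | about 7/4/3% | over 99% | 100% |
| Intercept, 3M reference | about 3-4% | 81/90/99% | 100% |
| Intercept, numeric dose | about 3-4% | 91/97/100% | 41/46/64% |
| 3M minus placebo | about 2.5% | about 2.5% | about 98% or more |

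Simulation error is within about a point or so. The intercept's slight excess over 2.5% in the first column arises because centring on the sample baseline mean adds variation that its standard error does not count.

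**The case against.** The strongest reply is that the damage is a wording slip. The models contain a dose term, so arm contrasts can be estimated. The sentence after the intercept rule already plans contrast intervals, and routes is probably leftover text for doses. The hypotheses are phrased as decreases and increases, and section 3.4 speaks of comparison with baseline (for PET CT), so a within-group summary may have been intended. The endpoints are exploratory, section 9.2 promises summary analyses only, and no success rule exists.

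Most of this stands, and it limits how serious the point is. It does not remove it. Reading routes as doses supplies 3 million versus 1 million/kg at best. A contrast with placebo is still not named, and the intercept is still the stated basis for each hypothesis. A within-group summary is legitimate description, but it makes no use of the concurrent placebo arm.

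A reader might infer that the plan makes the treatment comparison impossible, or that the trial will declare false efficacy. The documents support neither: the dose term can supply the contrasts, and nothing is declared on the strength of any interval. The percentages above should not be read as this trial's error rates either. Drift, effect size and correlation are assumed, and the plan's first-choice covariance is unstructured, with compound symmetry only as fallback.

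**Conclusion.** The point holds and should be fixed. Section 9 judges the ten Aim 1 hypotheses by a quantity that is not an arm comparison. It names no MSC-versus-placebo contrast, and it labels its one contrast by a factor that does not vary. The safety paragraph has the same fault: two routes and four groups do not match three IV arms.

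The core rests on the text and on the weights summing to 1. It needs only the change scale and centred baseline, and no assumed effect sizes. The illustration shows the possible size: with a shared drift of -0.5 SD and no MSC effect, about 81% to 99% of placebo-reference intercept intervals fall below zero, against about 2.5% for the contrast. With a -1 SD effect in both MSC arms and no drift, the intercept picks it up in anything from about 3% to 100% of trials, depending on coding.

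The intercept is not badly misleading in every case. With neither drift nor effect, its false-support rate is only modestly above nominal, up to about 7% under effect coding at the lowest correlation.

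**What to change.** In the Aim 1 paragraph of section 9, replace the intercept sentence with wording such as: *Each hypothesis is assessed by the least-squares-mean difference in change from baseline of each MSC dose versus placebo, and of 3 million versus 1 million MSCs/kg, with 95% CI, descriptive and not adjusted for multiplicity.* State that dose enters as a three-level factor, and put these arm contrasts in place of the reference to routes of administration.

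In the safety paragraph, replace the two routes of delivery with the same arm contrasts of proportions, and reconcile the four groups with the three arms.

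The cost is section 9 wording, with no new data. With one visit or one visit average per outcome, it yields 10 × 3 = 30 descriptive intervals. If there were no effects, about 30 × 0.05 = 1.5 would exclude zero by chance, and the report should say so. Reporting by visit would multiply that number. Visit terms and the choice of main visit or window are separate decisions for the sponsor, and this correction does not depend on them.

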9.1 Bias Minimization

All subjects meeting the specified eligibility criteria will be enrolled on a first-come basis.

9.2 Planned Analyses

The clinical study report will contain only summary data analyses reflecting safety profiles, and summary data analyses of efficacy. All patient data will remain coded during analyses to maintain patient confidentiality.

10. ADVERSE EVENT REPORTING

10.1 Adverse Events and Stopping Rules

Adverse events occurring during the enrollment period should be documented by the Investigator in progress notes, but will not be collected or analyzed by Indiana University School of Medicine unless considered serious by the Investigator. Adverse events will be reported according to federal guidelines for safety reporting for Investigational New Drug Application (IND).

Serious adverse events (SAEs) encountered during study enrollment will be documented by the Investigator and reported to Indiana University School of Medicine immediately upon discovery. SAEs are defined under current Good Clinical Practice (cGCP) guidelines as events that result in one or more of the following:

- life-threatening illness or injury;
- permanent impairment of a body structure or a body function;
- medically necessary in-patient hospitalization;
- medical or surgical intervention necessary to prevent permanent impairment to body structure or function; or
- fetal distress, fetal death, or congenital abnormality.

Serious events that affect the rights, safety, or welfare of subjects must be documented on a form and be reported immediately to Indiana University School of Medicine and to the Investigator’s IRB according to that IRB’s policies.

Major Adverse Cardiac Events (MACE). MACE endpoints will include: death, nonfatal myocardial infarction, including, Q-wave, non Q-wave, and CK/CKMB elevation, stroke, transient ischemic attack (TIA), hospitalization for heart failure, hospitalization for hypo or hypertension, life-threatening arrhythmia, and aneurysm rupture, which will be collected throughout the 6-month time period.

Severity Assessment. We will use the Common Terminology Criteria for Adverse Events (CTCAE), version 4.0, for detailed descriptions of Severity Grades. The CTCAE schema is classified by body system and event using the MedDRA hierarchy and provides descriptions of events that qualify under each severity rating.

The following table contains general descriptions of Adverse Event Severity Grades.

Severity Grade	Description
1	Mild. Asymptomatic or mild symptoms; clinical or diagnostic observations only; intervention is not indicated.
2	Moderate. Minimal, local, or non-invasive intervention indicated or limiting activities of daily living (i.e. preparing meals, shopping for groceries/clothes, managing money, using telephone, etc.)

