3.3 Proposed Intended Use Statement

Allogeneic MSCs are a novel therapeutic option to suppress growth of small AAA. Human MSCs are intended for investigational use only by selected investigators familiar with their use and experienced in conducting clinical studies. Human MSCs may only be administered to human subjects participating in clinical studies sponsored/approved by Indiana University School of Medicine, and who have provided formal written consent.

3.4 Study Objectives.

The principal objective of this study is as follows:

Assess the safety and efficacy of administration of allogeneic MSCs in patients with small AAA.

This study will test the hypothesis that administration of MSCs in doses of 1×10^6 MSCs/kg. and 3×10^6 MSCs/kg demonstrate safety in patients with small AAA. This trial will also test the hypothesis that MSCs, in a dose dependent fashion (1×10^6 MSC/kg. vs. 3.0×10^6 MSC/kg.), promote the frequency and immune suppressor function of Treg cells and decrease AAA inflammation as measured by computed tomography. In an double blinded, Phase I trial, 36 patients with AAA measuring 35-50 mm in maximal transverse diameter (MTD) will be randomized in a 1:1:1 fashion to receive intra-venously either a single dose of 1×10^6 MSCs/kg., 3×10^6 MSCs/kg. , or placebo (Plasmalyte A) (n =12/group). The primary safety endpoints will be incidence of treatment related adverse events accrued over 24 months. Efficacy measures are changes in frequency and immune suppressor function of Tregs, number and cytotoxic activity of CD4+/CD8+ CD28- T-cells, activated monocytes, and changes in aortic inflammation as measured by PET CT compared to baseline. Secondary endpoints measured out to year 5 will include changes in IL-10 and Tr1 levels. Duplex ultrasound measurements of the AAA, which is considered standard of care, will be recorded as change in aortic inflammation during long-term follow-up. Incidence of surgical intervention, aneurysm related death, quality of life, and major adverse cardiac events will be recorded through year five (5).

Completion of this study will determine if MSCs are safe in patients with AAA and provide critical insights that will direct a placebo-controlled, Phase II randomized trial.

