5.2.2 Duration of study activities

Enrollment is anticipated to continue for approximately 1–2 years. In the event that additional studies are going to be conducted, new protocols will be developed specifically for those studies.

5.3 Patient Selection. The eligibility criteria for prospective enrollment of subjects are shown in **Table 1**.

Table 1. Inclusion/Exclusion Criteria for Enrollment of Subjects

Inclusion criteria
	
 1. Be ≥ 40 and ≤85 years of age. 2. Have diagnosis of non-inflammatory degenerative infrarenal abdominal aortic aneurysms measuring 30-50mm. in diameter by Computed Tomography (CT) scan. 3. Females of childbearing potential must be willing to use one form of birth control for the duration of the study. Female participants must undergo a blood or urine pregnancy test at screening.

Exclusion criteria
	
 1. Inflammatory AAA defined by a thickened aortic wall and retroperitoneal fibrosis and adhesions of peritoneal organs, and elevated erythrocyte sedimentation rate or in the opinion of investigator. 2. Mycotic AAA defined as sacular morphology, a positive blood culture, fever, or in the opinion of the investigator. 3. Symptomatic, Saccular, or any AAA associated with thoracic aorta dilatation > 5.0 cm. 4. Infra-renal AAA associated with Marfan’s or Ehlers-Danlos Syndrome or other connective tissue disorders 5. Common or external iliac artery aneurysm > 30 mm. in maximal transverse diameter. 6. AAA due to dissection. 7. Allergy to iodine contrast. 8. History of untreated or recurrent cancer within the last 5 years, except basal cell skin carcinoma.

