6.1.4 Required training and MSC administration

MSCs will be manufactured at the Case Cancer Comprehensive Center Cellular Therapy Lab at Case Western Reserve University in Cleveland, Ohio with supervised and trained personnel. The MSCs, in the

appropriate dose, will be shipped to the Cell Therapy Laboratory at University Hospital where the MSCs will be thawed and diluted 1:1 with Plasmalyte A and administered within 4 hours of the thawing process. All personnel in the Stem Cell Laboratory are qualified in the processing on MSCs for patient administration. The thawed MSCs will then be administered to the patients in a monitored setting with telemetry and pulse oximetry.

MSC Administration. This is a randomized, double blinded trial and after enrollment, patients will be randomized in a 1:1:1 fashion to receive placebo (Plasmalyte A), 1×10^6 MSC/kg., or 3×10^6 MSC/kg. The rationale for selection of these doses was presented in the Research Strategy. IV MSC infusions will occur in a monitored inpatient room on the Surgical Intensive Care Unit at the Roudebush VA Hospital or the Clinical Research Center at IU Health University Hospital. Patients will be pre-medicated with hydrocortisone (25-50 mg. IV) and diphenhydramine (Benadryl, 25-50 mg. IV). All subjects will be monitored throughout the MSC infusion procedure with vital signs and pulse oximetry beginning 15 minutes prior to infusion and ending 2 hours post procedure. They will also be evaluated for clinical signs of pulmonary distress including progressive or sustained hypoxia, dyspnea, and tachycardia. If enrolled patients develop any of the following conditions within 24 hours of planned infusion, MSC delivery will be halted:

- a. Fever (Temperature increase to $\geq 100.4^\circ\text{F}$)
- b. Upper respiratory tract infection diagnosed by independent health provider.
- c. Significant shortness of breath
- d. Unanticipated change in consciousness or neurological change
- e. Major adverse cardiac event

All patients will be admitted for continued observation to the SICU at the Roudebush VA Hospital or the Clinical Research Center at IU Health University Hospital. The patient will be observed for two hours after the study product infusion and then discharged home. The patient will be re-examined on Days 7 and 14 for treatment related adverse events.

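### Section 10.1 excludes non-serious adverse events in an undefined enrollment period from collection and analysis, which contradicts the 24-month primary safety endpoint

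*Combined protocol and SAP*

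**What the plan says.** The synopsis states: "The primary safety endpoints will be incidence of treatment related adverse events at 24 months post MSC-administration". Section 3.4 repeats it: "The primary safety endpoints will be incidence of treatment related adverse events accrued over 24 months". Neither is limited to serious events. Section 9 likewise measures safety by treatment-related adverse events, sorted into three body systems (cardiovascular, respiratory, infectious) and two severity categories (SAE and MACE).

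The schedule supports that endpoint. Table 2 marks AE/SAE evaluations at all nine visits from Baseline to Month 24, and Table 3 at all six visits from Month 30 to Month 60. Section 6.1.4 adds: "The patient will be re-examined on Days 7 and 14 for treatment related adverse events". Section 10.1 adopts CTCAE version 4.0 grading, which includes mild and moderate events.

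Section 10.1 opens with a different rule: "Adverse events occurring during the enrollment period should be documented by the Investigator in progress notes", and these events "will not be collected or analyzed by Indiana University School of Medicine unless considered serious by the Investigator". The next paragraph uses a similar qualifier: "Serious adverse events (SAEs) encountered during study enrollment will be documented by the Investigator". For MACE, the same section gives a collection period: "which will be collected throughout the 6-month time period". Section 3.4 has major adverse cardiac events recorded through year five.

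**The concern.** The plan schedules visits to find these events and grades them by severity, then says the non-serious ones are neither collected nor analysed. Safety is the primary question of this Phase I comparison of two MSC doses with placebo. Section 11.1 names rash, mild fever and myalgia as the most notable risks and calls them mild, which is the kind of event the rule removes. A dose-related rise in mild or moderate reactions could go unreported even though patients were examined for it.

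The filter is also the investigator's judgement of seriousness. Section 4.2 leaves the PI unblinded, so if the PI makes that call, an unblinded judgement decides what enters the primary result.

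**Working it through.** There is no plan figure to reproduce, because the documents give no adverse event rate and no power calculation. The check is first a comparison of texts, then an illustration of size.

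**What the enrollment period could mean.** It is not defined, and usage varies.

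1. *Time on study.* Section 7.1 speaks of patients enrolled in the trial at month 12. On this reading only SAEs and the separately collected MACE reach the analysis. That contradicts the endpoint directly.
2. *The accrual window.* Section 5.2.2: "Enrollment is anticipated to continue for approximately 1–2 years". Whether an event counts then depends on the calendar date of entry.
3. *Before randomization.* Sections 6.1.4 and 7.1 place randomization after enrollment. The conflict with the post-infusion endpoint disappears, but the parallel SAE sentence would then also stop before infusion, and the Baseline AE evaluation in Table 2 still conflicts.

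**Size under reading 1.** From the synopsis: 12 patients per arm, so 24 on MSC. From section 9: Wilson 95% intervals. Assumed: non-serious related events occur at rate p on MSC, with no SAE or MACE.

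The rule then gives 0/24. The Wilson upper limit at zero is z²/(n + z²), with z² = 3.84:
- n = 24: 3.84/27.84 = 13.8%
- n = 12 (one arm): 3.84/15.84 = 24.2%

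Expected number omitted = 24p. Chance of omitting at least one patient = 1 − (1 − p)^24.

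| Assumed p | Expected omitted | Chance of at least one | Example with full collection (Wilson 95%) |
|---|---|---|---|
| 5% | 1.2 | 1 − 0.95^24 = 0.71 | 1/24: 0.7–20.2% |
| 10% | 2.4 | 1 − 0.90^24 = 0.92 | 2/24: 2.3–25.8% |
| 25% | 6 | 1 − 0.75^24 = 0.999 | 6/24: 12.0–44.9% |

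At 5% and 10% the interval for 0/24 still contains the true rate, so the loss is of observed events. At 25% the interval excludes the true rate.

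If instead some related events are serious, take an overall rate r of which 10% are serious. The chance that a 12-patient arm shows no collected event is (1 − 0.1r)^12: 0.89 at r = 10% and 0.74 at r = 25%. With full collection it is (1 − r)^12: 0.28 and 0.03.

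**Size under reading 2.** Assume uniform entry over A months. A patient's first 14 days (0.46 month) fall wholly inside the window with probability 1 − 0.46/A:
- A = 12: 0.962, or 34.6 of 36 patients
- A = 24: 0.981, or 35.3 of 36 patients

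Mean follow-up inside the window is A/2:
- A = 12: 6 of 24 months, 25%
- A = 24: 12 of 24 months, 50%

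Early reactions would be excluded for nearly everyone, and later events kept or dropped according to entry date.

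**Section 9.** Its three system categories can hold non-serious events, but there is no row for any treatment-related event, which is the stated primary endpoint. Rash and myalgia fit none of the five categories unless serious. Correcting section 10.1 alone would still leave them out of the tables.

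**The case against.** The best defence is reading 3. Besides sections 6.1.4 and 7.1, the exclusion criteria count days before enrollment and section 4.3 counts follow-up after it, so enrollment often looks like a pre-treatment step. The sentence would then exclude only non-serious events before infusion. Nor would all serious-event reporting lapse afterwards: section 10.1 also requires immediate reporting of serious events affecting subjects' rights, safety or welfare, and IND safety reporting, without an enrollment qualifier. This stands as far as it goes. It still leaves the general SAE sentence ending before infusion and the Baseline evaluation in conflict, so the section needs rewriting on this reading too.

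A second defence is that acute reactions are captured elsewhere. Table 2 has an infusion reaction assessment covering flushing, tachycardia, vital signs and oxygen saturation, and events in progress notes remain in source documents that the sponsor can inspect. That limits the loss, but section 9 links none of this to an analysis, and events recoverable from notes are not events in the primary result.

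Third, every rate above is assumed, 25% sits poorly with section 11.1's description of the risks as rare, and section 9 uses its intervals descriptively. All true. The contradiction does not depend on these figures.

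Finally, the MACE period and the missing section 9 row are separate defects. They belong in the same edit but add nothing to the severity of this point.

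**Conclusion.** The concern holds and must be fixed. Under the time-on-study or accrual reading, following section 10.1 means the primary safety endpoint cannot be computed as the synopsis and section 3.4 define it. Under the pre-randomization reading the endpoint survives, but the SAE sentence no longer works as intended. How much would be lost depends on the reading and on event rates that the documents do not give. If related events on MSC are non-serious at 5% to 10%, the expected omission is 1.2 to 2.4 of 24 patients. Confidence in the contradiction is high. The amount of data actually lost is uncertain, because sites might follow the visit schedule rather than section 10.1.

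**What to change.** Replace the section 10.1 rule with wording such as: *All adverse events, serious or not, from the day of study product administration (including pre-medication) through Month 24 are entered on the CRF with CTCAE v4.0 grade and relatedness, and are analysed.*

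In the same edit:
- Say how the Baseline and Month 30 to 60 evaluations are used.
- Define or delete the enrollment qualifiers in both the AE and the SAE sentences.
- State who judges relatedness and seriousness, on what scale, and whether that person is blinded.
- Reconcile the MACE collection period: 6 months in section 10.1, through year five in section 3.4.
- In section 9, add a row for any treatment-related adverse event and a summary by CTCAE grade across all body systems, keeping the five existing categories.

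The cost is protocol wording, two added summaries, an AE page on the CRF if there is none, and modest extra data entry for 36 patients. No visits are added, because the evaluations are already scheduled.
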